Study participants will be randomized to receive either DCS or placebo and stratified according to baseline expired CO level (10-20 ppm and >20 ppm).

a.1. Availability and Flow of Subjects into Treatment

After approximately 240 telephone screens, we plan to conduct in-person screens of 40 individuals in the course of 18 months to achieve our desired sample size. Based our prior smoking-related studies, we estimate that there will be approximately 16 potentially eligible participants per month from treatment programs at McLean Hospital and the other Boston area recruitment methods and an adequate flow of participants to meet our target of 2.5 participants per month.

a.2. Study Visits and Participant Payments. Each weekly visit over 10 weeks will include a 50-minute CBT session and dispensing of pills. Research assessments will take place at 4 and 10 weeks of treatment and 4 and 12 weeks post-treatment. See Table D.1, Schedule of Measures. Participants will earn \$50 for the initial screen, \$20 for each of the 10 Actiwatch/Diary visits, a \$10 gift card for the completion of additional neuropsychological assessments at week 3, \$50 for each of the 4 Follow-Up Interviews, and a bonus \$50 for diary completion, for a total of \$510. Medication and therapy will be provided at no cost.

a.3. Clinical Emergencies. If a participant is intoxicated, the participant will be evaluated medically, sent home in a taxi when safe, and the appointment re-scheduled. If a participant experiences a problem that requires clinical

intervention during the course of the study (e.g., mania, suicidal ideation, or dangerous intoxication), we will evaluate the situation medically, make an appropriate recommendation, and help the participant to implement this plan. This could involve hospitalization at McLean, referral to the hospital's outpatient program, or other medical or psychiatric treatment, as clinically appropriate.

b. Drugs to be used

b.1. D-cycloserine. D-cycloserine (DCS)(Seromycin®, The Chao Center, West Lafayette, IN) is an FDA-approved broad spectrum antibiotic for the treatment of tuberculosis.

Participants will be randomized to receive either placebo or DCS 250 mg, given 1 hour prior to weekly CBT sessions. The McLean Research Pharmacy will randomize the participants and dispense medication or placebo weekly to the study physician, who

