A relatively similar analytic approach will be used to assess the effect of DCS on changes in expired CO assessments. A linear mixed effects model will be used to assess changes in CO during treatment and at post-treatment follow-up. The linear mixed effects model will include the effects of treatment group, time and the baseline measure of CO; the inclusion of random effects accounts for the correlation among the 12 post-baseline CO measurements (1-per week during 10 weeks of treatment, plus week 14 and 22). We will adjust for the dose of NRT by including dose as an additional covariate in the linear mixed effects model analysis of the treatment comparison (DCS vs. placebo). The linear mixed effects model includes random intercepts and random slopes for time to appropriately account for correlation among repeated measures of CO and heterogeneity of variance over time; the model will be fit using PROC MIXED in SAS.

Analyses of secondary outcomes will focus on assessing the effect of DCS on neuropsychological assessments. For example, linear mixed effects models will also be used to analyze quantitative/continuous neuropsychological outcomes (e.g., MSIT response accuracy and times), with appropriate transformation (e.g., log transformation) of the outcome as necessary. To examine the effect of DCS on changes in neuropsychological performance during treatment, the linear mixed effects model will include the effects of treatment condition and the baseline measure of the neuropsychological outcome. Additional analyses of secondary outcomes will focus on the number of days of cigarette smoking during treatment and post-treatment follow-up. Frequency of days of cigarette use will be analyzed via a log-linear (or Poisson) regression model, controlling for pre-treatment frequency of days of cigarette use. Although log-linear regression methods are considered appropriate for the analysis of count or frequency data, in many biomedical applications, count data have variability that far exceeds that predicted by the Poisson distribution; we expect that days of cigarette use will not be an exception. This phenomenon, known as overdispersion, will be accounted for in the planned regression analysis through the inclusion of a

dispersion parameter. The log-linear regression analyses will be fit using PROC GENMOD in SAS.

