Proficiency in English is necessary for a long-term treatment study that includes 10 CBT sessions and ensures that the participants can properly convey any subtle side effects that relate to their safe participation in this study.

For guidance, refer to the following Partners policy:

Obtaining and Documenting Informed Consent of Subjects who do not Speak English

https://partnershealthcare-public.sharepoint.com/ClinicalResearch/Non-English_Speaking_Subjects.1.10.pdf

RECRUITMENT PROCEDURES

Explain in detail the specific methodology that will be used to recruit subjects. Specifically address how, when, where and by whom subjects will be identified and approached about participation. Include any specific recruitment methods used to enhance recruitment of women and minorities.

a. Inclusion Criteria. 1) Age range 18-65 years; 2) DSM-IV diagnosis of nicotine dependence, based on the Structured Clinical Interview for DSM-IV (SCID) (First et al. 1996); 3) express a desire to quit cigarette smoking within the next 30 days; 4) smokes greater than or equal to 10 cigarettes per day and less than or equal to 20 cigarettes per day; 5) an expired carbon monoxide (CO) determination greater than or equal to 10 ppm over ambient values; 6) for women of childbearing age, a negative pregnancy test at screening with agreement to use adequate contraception to prevent pregnancy and multiple subsequent pregnancy tests; 7) consent for us to communicate with their prescribing clinician; 8) furnish the names of 2 locators, who would assist study staff in locating them during the study period; 9) live close enough to McLean Hospital to attend study visits; 10) plan to remain in the Boston area for the next 4 months; and 11) are willing and able to sign informed consent.

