Exclusion Criteria. 1) Current diagnosis of other drug or alcohol dependence (other than nicotine and opioid dependent participants on agonist or antagonist pharmacotherapy); 2) significant cardiac disease; 3) current serious psychiatric illness or history of psychosis, schizophrenia, bipolar type I disorder (taking psychiatric medications, aside from wellbutrin, is not an exclusionary criterion); 4) have a current medical condition (including significant laboratory abnormalities, such as liver function tests >5 times the upper limit of normal range) that could prevent regular study attendance; 5) have mental retardation or organic mental disorder; 6) exhibit acutely dangerous or suicidal behavior; 7) are pregnant, nursing, or, if a woman of childbearing potential, not using a form of birth control judged by the Principal Investigator to be effective; 8) current NRT or other smoking cessation treatment; 9) current CBT for smoking cessation; 10) current smokeless tobacco use; 11) inability to read or write in English; 12) has epilepsy.

b. Source of subjects and recruitment methods

Forty participants ages 18-65 with DSM-IV diagnosis of nicotine dependence will be recruited from McLean Hospital outpatient programs and from the Boston area via newspaper advertisements, flyers, Craigslist online ads, clinician referrals, and word-of-mouth.

Provide details of remuneration, when applicable. Even when subjects may derive medical benefit from participation, it is often the case that extra hospital visits, meals at the hospital, parking fees or other inconveniences will result in additional out-of-pocket expenses related to study participation. Investigators may wish to consider providing reimbursement for such expenses when funding is available

Subject Payments. Participants will earn \$50 for the initial screen, \$20 for each of the 10 Actiwatch/Diary visits, a \$10 gift card for the completion of the additional neuropsychological assessments at week 3, \$50 for each of the 4 Follow-Up Interviews,

and a bonus \$50 for diary completion, for a total of \$510. Medication and therapy will be provided at no cost.

For guidance, refer to the following Partners policies:

Recruitment of Research Subjects

[https://partnershealthcare-public.sharepoint.com/ClinicalResearch/Recruitment Of Research Subjects.pdf](https://partnershealthcare-public.sharepoint.com/ClinicalResearch/Recruitment%20Of%20Research%20Subjects.pdf)

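### The smoking-days model adjusts only for pre-treatment smoking days, which the entry rules probably hold near their maximum, so the adjustment gains practically no precision (minor)

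*Combined protocol and SAP*

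**What the plan says.** The number of smoking days is listed among additional secondary analyses in section 8.2 a and is to be fitted with a log-linear or Poisson "regression model, controlling for pre-treatment frequency of days of cigarette use". A dispersion parameter is added for overdispersion. No other baseline covariate is named for this model, and the pre-treatment window is not defined.

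The plan's other models use different baseline terms. The logistic models for 7-day abstinence adjust for the randomisation stratum (baseline expired CO 10–20 or >20 ppm). The linear mixed model for expired CO adjusts for baseline CO and nicotine replacement dose. Neither adjustment is extended in writing to smoking days.

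Entry requires a DSM-IV diagnosis of nicotine dependence, and (Inclusion Criteria, items 4 and 5) that a person "smokes greater than or equal to 10 cigarettes per day and less than or equal to 20 cigarettes per day" and has "an expired carbon monoxide (CO) determination greater than or equal to 10 ppm over ambient values". Exclusion item 8 removes people on "current NRT or other smoking cessation treatment". Table D.1 schedules the Fagerstrom test and expired CO at baseline.

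**The concern.** Baseline adjustment helps precision only if the baseline measure varies between people and predicts the outcome. Dependent smokers of at least 10 cigarettes per day, not yet in treatment, will mostly have smoked on every day of any plausible look-back window. The covariate is then a near-constant column. If every value is equal, it duplicates the intercept and its slope cannot be estimated. If one or two people differ, they alone determine the slope.

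What is at stake is precision. With 40 participants, and a stated purpose of estimating an effect size for a larger trial, useful baseline information should not go unused when it is already being collected.

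**Working it through.** **The plan's own figure.** No power or precision is stated for smoking days. The only power statement (8.2 c) concerns 7-day abstinence: 80% power for a risk ratio of 2.48 at a within-person correlation of 0.5. Assuming three repeated assessments (weeks 10, 14 and 22), the effective n per arm is 20×3/(1+2×0.5) = 30. With rates of 0.25 and 0.62, the log odds ratio is 1.588 and its standard error is √[1/(30×0.25×0.75) + 1/(30×0.62×0.38)] = 0.565. Power is Φ(1.588/0.565 − 1.96) = 80.3%. The figure reproduces, and this point does not touch it.

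**Leverage.** First take intercept and covariate only: h = 1/40 + (x − x̄)²/SSx. The 30-day window is an assumption.
- One person at 25 days and 39 at 30: x̄ = 29.875, SSx = 24.375, h = 0.025 + 23.766/24.375 = 1.00.
- Two people at 25 and 38 at 30: x̄ = 29.75, SSx = 47.5, h = 0.025 + 22.5625/47.5 = 0.50 each.

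The next results come from the full design matrix with the treatment term, assuming a 28-day window.

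| Baseline days among 40 people | Result |
|---|---|
| All 28 | rank 2 of 3; slope not estimable |
| One at 24 | leverage 1.00 |
| Two at 24 | 0.50 each (same arm) or 0.53 each (different arms) |
| One at 26, one at 20 (different arms) | 0.11 and 0.94 |
| Typical daily smoker | about 0.05 |

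**Effect on the treatment comparison.** Quasi-Poisson models (Pearson scale) were fitted with and without the covariate, 400 simulated trials per scenario. The assumptions, none from the documents, are a 28-day baseline, 70 treatment days, a beta(1.0, 0.8) smoking propensity, non-daily smokers at 18–27 baseline days, and a smoking probability proportional to baseline days.

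| Non-daily smokers of 40 | Median deviance explained (90th percentile) | Median treatment SE, adjusted/unadjusted |
|---|---|---|
| 1 | 1.3% (7.9%) | 1.02 |
| 2 | 0.8% (7.8%) | 1.015 |
| 4 | 1.4% (9.2%) | 1.01 |
| 8 | 2.4% (11.8%) | 1.01 |
| Contrast: days spread over 10–28 | 19.6% (34.7%) | 0.89 |

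With two non-daily smokers, deleting the person with the highest leverage moves the slope by a median 1.2 SE (90th percentile 5.9). The treatment estimate moves by 0.07 SE (90th percentile 0.27). With one non-daily smoker, adding the covariate moves the treatment estimate by a median 0.11 SE (90th percentile 0.24).

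**What a varying covariate could give.** Let r be its correlation with the outcome (assumption). In the linear approximation the treatment SE is multiplied by √[(1 − r²)×38/37]:
- r = 0.3: √(0.91×1.027) = 0.97.
- r = 0.5: √(0.75×1.027) = 0.88.

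Take a standardised difference of 0.8 (assumption), 20 per arm and two-sided alpha 0.05. The noncentrality is 0.8/√(1 − r²) × √10:
- r = 0: 2.53, power 69%.
- r = 0.3: 2.65, power 73%.
- r = 0.5: 2.92, power 81%.

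These are noncentral-t values for a continuous outcome, not for the planned Poisson model.

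**The case against.** Near-constancy is nowhere documented. The window is undefined, 10 to 20 cigarettes per day could be an average that allows smoke-free days, and entrants want to quit within 30 days, so some may already have skipped days. This stands as a limit: the point is a probable consequence of the entry rules. The simulation softens it, since even 8 non-daily smokers in 40 bring no gain in the median treatment SE.

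A reader might infer from a leverage of 1.00 that the trial's result hangs on one person, or that the comparison is biased. The documents and the figures do not support that. The unstable quantity is the slope of a nuisance term, randomisation keeps the comparison valid, and the treatment estimate barely moves. If all baseline values are equal, the model simply returns the unadjusted effect. With exactly one non-daily smoker, the model fits that person perfectly, so the treatment estimate comes from the other 39. That is undesirable, but it does not contradict the intent-to-treat statement in 8.2 a, which is made for the primary analysis.

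The size of the gain also rests on assumptions. No document gives a correlation, a standardised difference or a power for this outcome, and at r = 0.3 the gain is only about 4 percentage points of power.

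Finally, cigarettes per day would be a doubtful replacement, because the entry rule confines it to 10–20. Baseline CO has a lower entry limit but no upper one, and stratifying at 20 ppm presupposes that it varies.

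**Conclusion.** The point holds as a minor one. If the entry rules keep pre-treatment smoking days at or near the ceiling, the planned adjustment explains a median of about 1–2% of deviance and leaves the treatment SE at 1.01–1.02 times its unadjusted value. The loss is the precision that a better covariate could have brought: about 3–12% off the SE if r is 0.3–0.5. No bias follows, neither primary analysis is affected, and no stated figure is contradicted. The conclusion depends on the inferred ceiling and on the simulation settings. The gain depends further on the assumed correlation and, for power, on the assumed difference of 0.8. The outcome is secondary in an exploratory pilot, which keeps the priority low.

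**What to change.** In the smoking-days paragraph of section 8.2 a, replace pre-treatment smoking days as the adjusting covariate with one pre-specified baseline measure that varies. Baseline expired CO or its randomisation stratum would match the plan's other models; the baseline Fagerstrom score is the alternative. Make the choice before unblinding. Define the look-back window for pre-treatment smoking days and report them descriptively by arm.

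The cost is one phrase in the analysis section and a sentence for the window. No new data, visits or participants are needed.

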will deliver a prescription to the pharmacy days in advance of the CBT session. The medication will be purchased from McKesson by the PI. The dose is based upon prior clinical trials of patients with psychiatric disorders (Norberg et al. 2008). Norberg et al. (2008) showed that timing of the dose significantly predicted effect size; their meta-analysis found that the greatest enhancement of animal extinction or human exposure therapy was seen when DCS was given immediately prior to or after extinction/exposure.

Participants will be assessed for side effects prior to each medication administration. If side effects preclude a participant from continuing study medication, the medication will be discontinued, but the participant will continue to be followed for follow-up assessment visits. While our group recognizes the importance of medication adherence in substance use disorder patients, the once-weekly dosing of DCS mitigates many adherence issues.

b.2. Nicotine Replacement Therapy. Transdermal nicotine patches delivering 21-, 14-, and 7-mg/24 hours will be purchased from CVS by the PI. Nicotine patches will be distributed to volunteers at the initial assessment session and at the 6- and 8-week follow-up sessions. Participants smoking 15 or more cigarettes per day will start with a 21-mg patch and those smoking 10-15 cigarettes per day or who cannot tolerate a 21-mg patch will start with a 14-mg patch. Participants starting with a 21-mg nicotine patch will use it daily for 6 weeks, followed by a taper to a 14-mg nicotine patch daily for 2 weeks and, finally, a 7-mg nicotine patch daily for 2 weeks. The others will start with a 14-mg patch used daily for 8 weeks followed by a 7-mg patch used daily for 2 weeks. We will discuss possible side effects of nicotine with volunteers and ask them to report these symptoms or any others they experience. Adverse event forms will document any side effects experienced while using the patch.

c. Devices to be used

N/A.

d. Research Measures: Data to be collected

d.1. Diagnostic Assessment of Smoking. To make the diagnosis of nicotine dependence, the Structured Clinical Interview for DSM-IV (SCID) (First et al. 1996) will be used.

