d.2. Self-Report of Smoking. Participants will receive a packet of 1 page, self-addressed, prepaid postage Daily Diary pages. The diary consists of questions about smoking and other drug use as well as eating and sleeping habits. We have had excellent compliance with these diaries in the past. During the weekly visits, we plan to collect cigarette use data using the Timeline Follow Back (TLFB) (Sobell and Sobell, 1992) protocol.

d.3. Alveolar carbon monoxide (CO). End-expiratory CO will be measured after a 10-second breath-hold using a P.K. Morgan CO analyzer (Chatham, Kent, UK) at baseline, each CBT session, and each follow-up visit. Abstinence from cigarettes will be verified by an expired air CO concentration ≤ 10 ppm.

d.4. Other Assessments. We developed the self-administered Drug and Alcohol Use Questionnaire (Weiss et al. 1988), a baseline measure that addresses the context of lifetime and recent drug and alcohol use, as well as sociodemographic data. Function in multiple spheres of the participants' lives will be obtained at baseline and monthly using the LIFE functional assessment (Keller et al. 1987). HIV risk behaviors will be assessed at baseline and weeks 10, 14, and 22 with the Risk Assessment Battery (Metzger 1992). To assess treatment services outside the study that patients use, we will administer the Treatment Services Review (TSR) (McLellan et al. 1992) at baseline and monthly. The Client Satisfaction Questionnaire (CSQ-8) is an 8-item self-report scale will assess satisfaction with treatment. The Quick Inventory of Depressive Symptomatology (QIDS-SR) is a short self-report questionnaire for depressive symptoms used successfully in the STAR*D project. At baseline and week 3, several standard self-report questionnaires will be used to assess cigarette craving: Tiffany QUS Brief form, nicotine withdrawal: Wisconsin Smoking Withdrawal Scale, and affect: Positive and negative affect scales (PANAS). Menstrual cycle phase information also will be collected in women.

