b. Missing Data and Dropout. With repeated assessments, missing data are inevitable. Incomplete data pose 2 concerns for inference: bias and efficiency. We will use statistical methods (GEE and linear mixed effects models) that incorporate partially observed data on participants who drop out. We will provide detailed descriptions of the patterns of missing data and assess the sensitivity of results to different assumptions about the mechanism by which data are missing. For example, pattern-mixture models can be used to assess the sensitivity of results to informative dropout or missing data. [name], our biostatistician consultant, is an expert in handling missing data in longitudinal studies (Fitzmaurice et al. 2004).

c. Sample Size and Power. We plan to randomize 20 participants per group for a total of 40 subjects. This sample size will provide a reasonable estimate regarding the effect size for a subsequent larger trial. With a total of 40 participants, and assuming a Type-I error level (alpha-level) of 0.05 (two-sided), a 7-day abstinence prevalence of 25% in the placebo group, the study would have approximately 80% power to detect medium effect sizes, corresponding to risk ratios of 2.3-2.6 (as the within-participant correlations ranges from 0.3-0.7). For example, with moderate within-participant correlation ($\rho=0.5$), the study would have 80% power to detect a risk ratio of 2.48.

For studies involving treatment or diagnosis, provide information about standard of care at Partners (e.g., BWH, MGH) and indicate how the study procedures differ from standard care. Provide information on available alternative treatments, procedures, or methods of diagnosis.

The standard of care for nicotine dependence is psychotherapy and/or medication; our treatment attempts to strengthen the best available treatment by enhancing the behavioral intervention.

Describe how risks to subjects are minimized, for example, by using procedures which are consistent with sound research design and which do not unnecessarily expose subjects to risk or by using procedures already being performed on the subject for diagnostic or treatment purposes.

Care will be taken to minimize risk. In addition to carefully screening prior to enrollment, we have weekly visits during which we will carefully monitor response to medication or placebo with respect to side effects and changes in mood.

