Describe explicitly the methods for ensuring the safety of subjects. Provide objective criteria for removing a subject from the study, for example, objective criteria for worsening disease/lack of improvement and/or unacceptable adverse events. The inclusion of objective drop criteria is especially important in studies designed with placebo control groups.

Safety Monitoring.

D-cycloserine has been shown to have a favorable safety profile in studies; it has been well-tolerated in several clinical trials and no adverse events have been reported (Santa Ana et al. 2009; Storch et al. 2010; Evans and Drobos, 2008; Goff et al. 2008).

Nonetheless, we will monitor safety through standardized methods. Presence and severity of side effects will be obtained through a standard Adverse Events Checklist as well as the "Frequency and Intensity of Side Effects Rating/Global Report of Side

Effects Burden” (Weiss, 2004), a 2-minute questionnaire that assesses the frequency, intensity, and level of burden of side effects. We will have a low threshold for obtaining additional medical workup during the study if the participant reports medical symptoms. Based on the literature on the effects of DCS, we anticipate few adverse events (Norberg et al. 2008). However, if a participant has a clinically significant laboratory or other medical abnormality that cannot be attributed to another cause, the participant’s medication will be discontinued and the participant will be followed for follow-up assessment visits only. If a participant is intoxicated, he/she will be evaluated medically, sent home in a taxi when safe, and the appointment rescheduled. If a participant experiences a problem that requires clinical intervention during the course of the study (e.g., mania, suicidal ideation, or dangerous intoxication), we will evaluate the situation medically, make an appropriate recommendation, and help the participant to implement this plan. This could involve hospitalization at McLean, referral to the hospital’s outpatient program, or other medical or psychiatric treatment, as clinically appropriate.

FORESEEABLE RISKS AND DISCOMFORTS

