Provide a brief description of any foreseeable risks and discomforts to subjects. Include those related to drugs/devices/procedures being studied and/or administered/performed solely for research purposes. In addition, include psychosocial risks, and risks related to privacy and confidentiality. When applicable, describe risks to a developing fetus or nursing infant.

a. Drug side effects and toxicities

D-cycloserine has been shown to have a favorable safety profile in studies; it has been well-tolerated in several clinical trials and no adverse events have been reported in these studies (Santa Ana et al. 2009; Storch et al. 2010; Evans and Drobos, 2008; Goff et al. 2008). Most adverse reactions occurring during therapy with D-cycloserine involve the nervous system or are manifestations of drug hypersensitivity (Seromycin package insert). Nervous system side effects appear to be related to higher doses (500 mg daily or above) and include drowsiness, headache, tremor, psychoses, and hyperirritability. Sudden development of congestive heart failure has been reported in patients receiving 1 to 1.5 g of D-cycloserine daily. Nicotine can cause headache and skin irritation.

b. Psychosocial risks

There is a low likelihood that participants previously screened for significant psychiatric disorders will be triggered by content of therapy sessions. As mood may be affected, we will monitor mood and suicidal ideation weekly with the Columbia Suicide Severity Scale.

EXPECTED BENEFITS

Describe both the expected benefits to individual subjects participating in the research and the importance of the knowledge that may reasonably be expected to result from the study. Provide a brief, realistic summary of potential benefits to subjects, for example, “It is hoped that the treatment will result in a partial reduction in tumor size in at least 25% of the enrolled subjects.” Indicate how the results of the study will benefit future patients with the disease/condition being studied and/or society, e.g., through increased knowledge of human physiology or behavior, improved safety, or technological advances.

a. Potential benefits to participating individuals

Participants may be able to stop or reduce their smoking, which would have enormous health and financial benefit to them.

b. Potential benefit to society

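### After a pill stop for an unexplained abnormality, the rule of follow-up assessment visits only, read literally, drops some weekly adverse-event, suicidality and CO checks

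*Combined protocol and SAP*

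**What the plan says.** The stopping rule appears twice in the same terms, under Safety Monitoring in the methods for ensuring subject safety and again under Data and Safety Monitoring. It applies to a clinically significant laboratory or other medical abnormality with no other attributable cause: "medication will be discontinued and the participant will be followed for follow-up assessment visits only". Section b.1 (D-cycloserine) has a parallel rule for side effects that prevent continued dosing: "the medication will be discontinued, but the participant will continue to be followed for follow-up assessment visits". That rule lacks the word *only*, but it does not promise weekly visits either.

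The weekly checks are set elsewhere:

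- Table D.1 lists adverse events and side effects, CO and the daily diary at baseline and weekly.
- Under Psychosocial risks: "we will monitor mood and suicidal ideation weekly with the Columbia Suicide Severity Scale".
- In the answer on how risks are minimized: "we have weekly visits during which we will carefully monitor response to medication or placebo with respect to side effects and changes in mood".
- Section d.3 takes CO "at baseline, each CBT session, and each follow-up visit".

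The term for the retained visits is never defined. Section a.2 (Study Visits and Participant Payments) states: "Research assessments will take place at 4 and 10 weeks of treatment and 4 and 12 weeks post-treatment". It also pays $50 "for each of the 4 Follow-Up Interviews", as does Subject Payments under Recruitment Procedures. Section b.2 hands out patches "at the initial assessment session and at the 6- and 8-week follow-up sessions". Table D.1 places its assessment battery at weeks 10, 14 and 22. The Overview dates follow-up assessments at 1 and 3 months after treatment, which corresponds to weeks 14 and 22.

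**The concern.** The word *only* limits contact at the point where a participant has just shown a possibly drug-related abnormality. Read literally, that person would have fewer scheduled adverse-event and suicidality checks than participants who are still taking the pill. Part of the reason for watching mood does not end with the pill: the Informed consent section links it to stopping nicotine.

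What is at stake is mainly participant safety. A secondary cost is that CO values go missing because of a safety event, in a trial whose primary analysis includes everyone randomized.

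**Working it through.** **Checking the plan's own figures.** Section 8.2 a gives 12 post-baseline CO measurements. Weeks 1 to 10 (10) + week 14 + week 22 = 12, which agrees. Section a.2 gives total payments of $510: 50 + 10 × 20 + 10 + 4 × 50 + 50 = 510, which also agrees. The 4 Follow-Up Interviews are therefore paid separately from the 10 weekly visits, and their number matches the four research assessments at weeks 4, 10, 14 and 22. Section d.3 likewise separates CBT sessions from follow-up visits.

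**Possible meanings of the retained visits.**

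- R1: weeks 4, 6, 8, 10, 14, 22 (a.2 plus the b.2 patch sessions)
- R2: weeks 4, 10, 14, 22 (a.2)
- R3: weeks 10, 14, 22 (Table D.1)
- R4: weeks 14, 22 (Overview)

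**Weekly checks lost.** If the pill is stopped after week *k*, the weekly checks still due number 10 − *k* (weeks *k* + 1 to 10). The number lost is that total minus the retained visits falling in those weeks. This assumes that the adverse-event and suicidality checks are done at the retained visits through week 10, which the documents do not state.

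| Stop after week | Checks still due | Lost, R1 | Lost, R2 | Lost, R3 | Lost, R4 |
|---|---|---|---|---|---|
| 1 | 9 | 5 | 7 | 8 | 9 |
| 4 | 6 | 3 | 5 | 5 | 6 |
| 6 | 4 | 2 | 3 | 3 | 4 |
| 8 | 2 | 1 | 1 | 1 | 2 |
| 9 | 1 | 0 | 0 | 0 | 1 |

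For example, after week 4 the checks due are at weeks 5 to 10. R1 keeps weeks 6, 8 and 10, so 6 − 3 = 3 are lost. R2 and R3 keep week 10 only, so 6 − 1 = 5 are lost. R4 keeps none, so all 6 are lost.

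**Wait to the next retained visit after a week-4 stop.** R1: 6 − 4 = 2 weeks. R2 and R3: 10 − 4 = 6 weeks. R4: 14 − 4 = 10 weeks. Under the weekly schedule the wait is 1 week.

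**CO values.** Weeks 14 and 22 are kept under all four readings, so the number of CO values lost equals the number of weekly checks lost. After a week-4 stop, 12 − 4 = 8 values are still planned, of which 3 to 6 are lost.

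**The case against.** The strongest reply is that nothing in the protocol says outright that weekly visits end. Section a.2 makes each weekly visit one event with a CBT session and pill dispensing, and no section says whether CBT continues after a pill stop. If it does, the participant still attends weekly and CO is taken at each session. Section 8.2 a also promises efforts to keep assessing people who leave treatment. This stands in part: the loss is an inference from the word *only*. But the 8.2 a promise gives no visit frequency and does not override a specific limit that is stated twice.

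Second, some checks are tied to dosing. Section b.1 assesses side effects before each dose, and the weekly visits are described as monitoring the response to pill or placebo. Fewer checks off drug could be deliberate. However, Table D.1 and the suicidality statement set weekly checks without making them depend on the pill, and no rationale for reducing them is given.

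Third, few people should be affected, and this stands. The protocol expects few adverse events. It links nervous-system effects to 500 mg daily or more, against 250 mg once weekly here. Scheduled post-baseline laboratory tests and ECG begin at week 10, when no weekly visits remain to be lost. An earlier laboratory trigger would need unscheduled testing, although the rule also covers other medical abnormalities.

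A reader might infer that a stopped participant has no contact at all until the next assessment. The documents do not support that. Monthly LIFE, Treatment Services Review and pregnancy tests, patch hand-out at weeks 6 and 8, medical work-up when symptoms are reported, on-call cover and notified outside clinicians may all remain. None of these is a scheduled weekly adverse-event or suicidality check.

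**Conclusion.** The point holds as a literal reading of a stated rule. Under each of the four meanings that the documents allow, a participant stopped early in treatment loses some weekly checks. After a week-4 stop the loss is 3 to 6 of 6, assuming that checks are done at the retained visits. By a week-9 stop it is 0 or 1 of 1. The choice of reading changes the count but not the conclusion for early stops.

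A reader might go further and conclude that the CO analysis is materially weakened. The documents do not support this. They give no rate of such stops and no within-person correlation for CO. The range of 0.3 to 0.7 in section 8.2 c is given for 7-day abstinence and should not be borrowed for CO. Neither precision loss nor bias can be quantified.

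This is a worthwhile, low-cost improvement for safety and for completeness of intent-to-treat data. It is not a flaw that threatens the trial's result.

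**What to change.** Delete *only* from the rule in both places (Safety Monitoring, and its repeat under Data and Safety Monitoring). In those two places and in section b.1, add:

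> Stopping the study pill does not end weekly visits: CO, Timeline Follow Back/diary, adverse-event and suicidality checks continue weekly through week 10, and the week 14 and 22 assessments (including CO) take place as scheduled, in both arms.

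This is a wording amendment. The weekly visits and their $20 payments are already within the $510 total. For a stop after week 4, the 3 to 6 restored visits come to 3 × $20 = $60 up to 6 × $20 = $120 per participant, with nothing added to the budget. The downside is small: some participants may decline weekly visits once the pill is stopped.
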